## 9 STUDY SCHEDULE AND PROCEDURES

The study consists in the following procedures:

- Subject enrolment,
- First study procedure (vascular embolization procedure using the mixture Lipiodol® Ultra Fluid associated with surgical glue) that may occur on the same day or within 7 days after the subject enrolment,
- An optional second study procedure if done within 30 days after the first one,
- A safety follow-up within 30 +/- 3 days after the last procedure using Lipiodol® Ultra Fluid associated with surgical glues that could be a visit, a phone call or completed with available medical records.

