### 9.1 Enrolment Visit

After the site staff has checked the eligibility criteria, the informed consent will be retrieved as described in section 13.3 and the following information will be collected:

- Demographic data: age, sex, height, weight
- Inclusion and non-inclusion criteria verification
- Medical history: past and current diseases (if relevant for the study) including allergies
- Indication for the vascular embolization procedure: number of lesions to be treated, lesion type and location
- Therapeutic/palliative strategy for the lesions to be treated: previous procedure, and if a second vascular embolization procedure using Lipiodol® Ultra Fluid in association with surgical glues is scheduled within the next 30 days after the first one, the next procedure scheduled after study procedure(s), target percent obliteration for the first study procedure (evaluated according to 4 level-score: 1. <50%; 2. 50-75%; 3. 75-99%; and 4. 100% corresponding to a complete nidus obliteration rate)
- Safety information: adverse event(s) whether serious or not. For more information on safety reporting, refer to Section 10
- Concomitant medications

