  - Fatal: this AE caused or directly contributed to subject's death.
- **Action taken with regard to administration of the mixture:**
  - No action: for AE occurring during the pre-treatment/procedure or post-treatment/procedure period, or if the mixture dosing/administration remained the same in spite of AE being present.
  - Study products withdrawn: the mixture was not administered or was stopped.
- **Other action taken:**
  - AE-targeted medication: the subject took a medication (either prescription or non-prescription) specifically for this AE. The medication(s) should be reported in the appropriate section of the CRF ("concomitant drug" section)
  - Other AE-targeted action: subject used other therapeutic measures (e.g. ice, heating pad, brace, cast...) or subject underwent a procedure (physiotherapy, additional laboratory test...) for this AE. The therapeutic measure(s) should be reported in the appropriate section of the CRF ("Action other than drug administered for the AE" section)
- **Assessment of the seriousness of the AE:** see Section 10.2 for serious adverse event (SAE) definition.

 CONFIDENTIAL	Protocol No. LUF-44-001 Version No. 3.0 Date January 20 th 2017	Page 28 / 43
---	--	--------------

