### 12.3 Safety Data

**Extent of exposure data** will be summarized per patient, per procedure and if necessary per administration: Number of procedures, reason for having a second procedure, subject duration of participation, number of injections, total volume and ratio of mixture, volumes of Lipiodol® Ultra Fluid and of the glues will be calculated, glues brand name, punctures sites, catheter flush done, other embolization material used and duration from first injection up to the time leaving the catheterization laboratory.

**Concomitant medication, material and procedures** administered during the subject participation will be summarized: Concomitant medications, additional embolization material introduced during study procedures and any new therapeutic/palliative procedure reported at follow-up will be

 CONFIDENTIAL	Protocol No. LUF-44-001 Version No. 3.0 Date January 20 th 2017	Page 34 / 43
---	--	--------------

summarized. Concomitant medications will be coded using the WHODrug dictionary and tabulated by ATC codes.

**Safety variables** collected for this study are the following; descriptive statistics will be performed on these data.

For the primary evaluation criterion, the following parameters will be described on adverse events related to the mixture (ADRs) occurring per study procedure(s):

- Number and percentage of subjects experiencing at least one ADR
- Number and percentage of ADRs
- Number and percentage of subjects experiencing at least one serious ADR
- Distribution by System Organ Class and preferred term (MedDRA Dictionary): number and percentage of subjects experiencing at least one ADRs and number and percentage of ADRs
- Number and percentage of ADRs according to their intensity and outcome
- Number and percentage of subjects treated for an ADR
- Number and percentage of subjects with mixture administration withdrawal due to ADRs

For the secondary evaluation criterion, ADRs descriptions will be repeated with all ADRs occurring in the whole subject participation period (Study procedure (s) and follow-up period).

Adverse events parameters will be collected as described in section [10.1.3](#) during the study procedure(s) and during the follow-up period.

For the secondary evaluation criteria related to AEs, all parameters will be described (secondary safety criteria):

- Number and percentage of AEs
- Number and percentage of subjects experiencing at least one AE

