#### 5.6.2.1 Primary analysis of the primary criteria

The following parameters will be described on ADRs occurring, per study procedure, after administration of Lipiodol® Ultra Fluid in association with surgical glues and before catheterization laboratory discharge (i.e

CONFIDENTIAL	STATISTICAL ANALYSIS PLAN N° LUF-44-001  VERSION N° 2.0	Page 18 / 29
--------------	---	--------------

ADR start date is greater or equal to time of first injection and lower or equal to time leaving the catheterization laboratory):

- Number and percentage of subjects experiencing at least one ADR,
- Number of ADRs,
- Distribution of number of ADRs per subject (1/2/3 or more),
- Number and percentage of subjects presenting with at least one ADR per intensity,
- Number of ADRs according to their intensity,
- Number and percentage of subjects presenting with at least one ADR per outcome,
- Number of ADRs according to their outcome,
- Number and percentage of subjects presenting with at least one ADR requiring an ADR-targeted medication,
- Number of ADRs requiring an ADR-targeted medication,
- Number and percentage of subjects presenting with at least one ADR requiring another ADR-targeted action,
- Number of ADRs requiring another ADR-targeted action,
- Number and percentage of subjects presenting with at least one ADR per lesion location,
- Number of ADRs per lesion location,
- Number and percentage of subjects presenting with at least one ADR per lesion type,
- Number of ADRs per lesion type,
- Number and percentage of subjects with mixture administration withdrawal due to at least one ADR,
- Number of ADRs leading to discontinuation of mixture administration,
- Number of ADRs leading to premature discontinuation,
- Number and percentage of subjects presenting with at least one serious ADR, whatever the seriousness criteria,
- Number of serious ADRs, whatever the seriousness criteria,
- Number and percentage of subjects presenting with at least one serious ADR per seriousness criteria,
- Number of serious ADRs per seriousness criteria.

The following distributions, by SOC and PT, will be tabulated on ADRs occurring, per study procedure, after administration of Lipiodol® Ultra Fluid in association with surgical glues and before catheterization laboratory discharge (i.e ADR start date is greater or equal to time of first injection and lower or equal to time leaving the catheterization laboratory):

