#### 5.6.2.4 *Analysis of secondary criteria*

The primary analysis of the primary criteria will be repeated with all ADRs occurring between catheterization laboratory discharge (the last one, if applicable) and end of follow-up period (see 5.6.2.1). The same analysis will be performed with all ADRs occurring from the first administration of the mixture up to the end of follow-up period. (see also 5.6.2.1).

Moreover, the following parameters will be described on AEs occurring, per study procedure, after administration of Lipiodol® Ultra Fluid in association with surgical glues and before catheterization laboratory discharge:

- Number and percentage of subjects experiencing at least one AE,
- Number of AEs,
- Distribution of number of AEs per subject (1/2/3 or more),
- Number and percentage of subjects presenting with at least one AE per intensity,
- Number of AEs according to their intensity,
- Number and percentage of subjects presenting with at least one AE per outcome,
- Number of AEs according to their outcome,
- Number and percentage of subjects presenting with at least one AE requiring an AE-targeted medication,
- Number of AEs requiring an AE-targeted medication,
- Number and percentage of subjects presenting with at least one AE requiring another AE-targeted action,
- Number of AEs requiring another AE-targeted action,
- Number and percentage of subjects experiencing at least one AE leading to discontinuation of mixture administration,
- Number of AEs leading to discontinuation of mixture administration,
- Number of AEs leading to premature discontinuation,
- Number and percentage of subjects presenting with at least one AE related to the mixture (ADR), at least one AE related to the study procedure and at least one AE related to the mixture and related to study procedure,
- Number of AEs related to the mixture (ADR), related to the study procedure and related to the mixture and to study procedure,
- Number and percentage of subjects presenting with at least one serious AE, whatever the seriousness criteria,
- Number of serious AEs, whatever the seriousness criteria,
- Number and percentage of subjects presenting with at least one serious AE per seriousness criteria,
- Number of serious AEs per seriousness criteria.

The following distributions, by SOC and PT, will be tabulated on AEs occurring, per study procedure, after administration of Lipiodol® Ultra Fluid in association with surgical glues and before catheterization laboratory discharge:

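### Protocol 10.1.3 defines two overlapping codes for action on the mixture, so an event that leads to a scheduled second procedure not being done may be missed in the withdrawal rows

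*Protocol*

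**What the plan says.** Protocol 10.1.3 asks the investigator to record, for each AE, the action taken on the mixture. There are two codes.

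- *No action* has two alternative limbs. The first depends on timing: "No action: for AE occurring during the pre-treatment/procedure or post-treatment/procedure period". The second depends on consequence: "or if the mixture dosing/administration remained the same in spite of AE being present".
- *Study products withdrawn* depends only on consequence and carries no limit on timing: "Study products withdrawn: the mixture was not administered or was stopped".

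A subject may have two study procedures. Protocol section 9 lists "An optional second study procedure if done within 30 days after the first one". Protocol 9.1 records at enrolment "if a second vascular embolization procedure using Lipiodol® Ultra Fluid in association with surgical glues is scheduled within the next 30 days", and SAP 5.4.8.2 tabulates that item.

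Withdrawal of the mixture is a planned safety output. Protocol 12.3 lists "Number and percentage of subjects with mixture administration withdrawal due to ADRs" and a parallel row for AEs. SAP 5.6.2.1 includes "Number of ADRs leading to discontinuation of mixture administration", together with the number of subjects and a breakdown by SOC and PT. SAP 5.6.2.4 then extends these rows: "The primary analysis of the primary criteria will be repeated with all ADRs occurring between catheterization laboratory discharge" (the last discharge, if there were two) and the end of follow-up, and again for the whole period from first administration. It does the same for AEs.

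**The concern.** A mixture-related event between the first procedure and a scheduled second one may be the reason the second is not done. That event is post-procedure, so the timing limb of *No action* applies. The mixture was also not administered because of it, so *Study products withdrawn* applies too. The protocol does not say which code takes precedence, and it does not define the post-procedure period for a subject who is due a second procedure.

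At stake is the meaning of one set of planned safety rows. A zero in the post-discharge withdrawal row could mean that no event stopped further treatment. It could also mean that sites followed the timing wording, under which no other value is possible. A reader of the study report could not tell which. If sites coded differently, the count would partly reflect site habit.

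**Working it through.** The documents state no figure on this point, so there is none to reproduce. The check is mainly one of definitions.

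**Step 1: which window the event falls in.** Suppose the second procedure is scheduled at enrolment and then not performed because of an ADR after the first. The subject has only one catheterization laboratory discharge, so the first is also the last. The ADR therefore falls in the SAP 5.6.2.4 window from last discharge to end of follow-up, and also in the whole-period window.

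**Step 2: what each reading gives.**

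| Reading | Code for this ADR | Post-discharge withdrawal row | Whole-period withdrawal row |
|---|---|---|---|
| Timing limb prevails | No action | Always 0, since every event in the window is post-procedure | Omits this case; stops during a procedure still count |
| Consequence prevails | Study products withdrawn | Can exceed 0 | Includes this case |
| Sites differ | Either | Depends on site | Depends on site |

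**Step 3: who is affected.** Once a subject has had the last planned procedure, no mixture remains to be withheld, and zero is correct on either reading. The overlap matters only where a planned second procedure was not done because of an event. A cancelled first procedure raises the same coding question, but that subject was never injected, is outside the Treated Set, and enters none of these rows.

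**Step 4: possible size, on assumed rates only.** The documents give neither the share of subjects with a second procedure scheduled nor the share cancelled for an event. Expected cases = subjects with a second procedure scheduled × proportion cancelled for an ADR.

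- Assuming 10% to 30% of 125 scheduled and 5% to 10% of those cancelled: 125 × 0.10 × 0.05 = 0.6, up to 125 × 0.30 × 0.10 = 3.75.
- Assuming 6 to 25 subjects scheduled (about 5% to 20% of 125) and 2% to 10% cancelled: 6 × 0.02 = 0.12, up to 25 × 0.10 = 2.5. The chance of at least one case is 1 − (1 − c)^m, where m is the number scheduled and c the proportion cancelled. It runs from 1 − 0.98^6 = 11% to 1 − 0.90^25 = 93%.

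Taken together, these give about 0 to 4 cases.

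**Step 5: effect on the row.** Assume 125 treated subjects. Under the timing reading the post-discharge row is 0/125 = 0.0% (exact 95% interval 0 to 2.9%). One recorded case would make it 1/125 = 0.8% (0.02 to 4.4%), and three would make it 3/125 = 2.4% (0.5 to 6.9%). The intervals (Clopper-Pearson) are added for scale; the plan itself is descriptive.

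**The case against.** A reader might infer that the protocol obliges sites to code *No action*, so that the post-discharge rows are zero by definition. The documents do not support this. *Study products withdrawn* has no timing limit and fits a second procedure that was not performed. Letting the timing limb always win would also deprive its wording about non-administration of most of its use. Where two codes both fit, neither is compulsory. This part of the objection stands.

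A reader might also infer that these events vanish from the safety report in the product's favour. They do not. The ADR or AE still counts in the tables by subject, event, SOC and PT, intensity, outcome and seriousness, and it appears in the listings. Only its action attribute may be wrong. The primary criterion, ADRs before leaving the catheterization laboratory, does not use this field. This also stands.

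It can be said that other outputs would reveal the case. SAP 5.4.8.2 and 5.6.1 together show second procedures scheduled and performed, SAP 5.6.2.1 counts ADRs leading to premature discontinuation, and Protocol 11.2 lists cancellation of the scheduled procedure among the discontinuation reasons. This stands only in part. The first comparison shows an aggregate gap without linking it to an event. Under Protocol 11.2, participation for anyone given the mixture ends at the end of follow-up, so a subject whose second procedure is cancelled can still complete the study. The cancellation reason does not say whether it covers a second procedure. The protocol collects the reason for having a second procedure but lists none for not having one.

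Finally, the visible SAP text does not name the field behind the withdrawal rows, parts of the SAP are not available, and no eCRF guide is supplied. A rule that resolves the overlap may exist there and cannot be excluded.

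**Conclusion.** The concern holds as a coding ambiguity with a limited effect. Protocol 10.1.3 mixes a rule by timing with a rule by consequence, and an event that leads to a scheduled second procedure not being done satisfies both. The withdrawal rows for the post-discharge and whole-period windows therefore cannot be interpreted reliably: they omit such cases if sites follow the timing limb, and depend on the site if practice differs. No other planned count is touched. The size, about 0 to 4 of 125 subjects, rests wholly on assumed scheduling and cancellation rates. The conclusion about the codes does not depend on those rates. It is worth correcting because a zero in a withdrawal row is easily read as reassurance, and the correction is cheap.

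**What to change.** Make the two codes mutually exclusive, by consequence.

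- *No action*: only when no ongoing or scheduled administration of the mixture was changed because of the AE.
- *Study products withdrawn*: when an ongoing injection was stopped, or a scheduled second procedure was not performed, because of the AE, whatever the period of onset.

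This changes how an event is recorded, not how any subject is managed.

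At data review, compare second procedures scheduled at enrolment (SAP 5.4.8.2) with those performed (SAP 5.6.1). For each subject whose scheduled second procedure was not done, query any AE coded *No action*. Both fields are already collected. The check cannot find a second procedure that was planned only after enrolment and then dropped; for those, the clearer code definitions are the only safeguard.

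The cost is a few data queries and a line of eCRF guidance. Changing the protocol text is the alternative, but Protocol 13.2 requires ethics committee and authority approval before a modification takes effect, so the guidance and query route is the more practical one.

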## 10.2 Serious Adverse Event

### 10.2.1 Definition of Serious Adverse Event

A Serious Adverse Event (SAE) is any untoward medical occurrence that at any dose:

- Results in death
- Is life-threatening
- Requires hospitalization or prolongation of existing in subject's hospitalization
- Results in persistent or significant disability or incapacity
- Is a congenital anomaly or birth defect
- Is medically important: adverse events that are not immediately life-threatening or do not result in death or hospitalization but may jeopardize the subject or may require intervention to prevent one of the other outcomes listed in the definition above, should also be considered serious.

Life-threatening in the definition of a serious adverse event refers to an event in which the subject was at risk of death at the time of event; it does not refer to an event which hypothetically might have caused death if it was more severe.

Medical judgment should be exercised in deciding whether an adverse event/reaction is serious in other situations. In case of a SAE, the investigator is responsible for the measures to be taken to ensure the safety of the study participants.

The following safety issues qualify for immediate reporting to Guerbet since they may alter the current benefit-risk assessment of the mixture, or would be sufficient to consider changes in the mixture administration or in the overall conduct of the study:

- Any serious and/or unexpected adverse event that occurs after the subject has completed the study and that is considered as related to the mixture by the investigator (causality not excluded).
- Any new event likely to affect the safety of the subjects and that may be related to the conduct of the study such as:
  - A SAE which could be associated with the study and which could modify the conduct of the study;
  - A significant hazard such as an unusual failure in efficacy;

Any suspicion of transmission of an infectious agent via the mixture should be considered as a serious and processed as an SAE.

In addition, any adverse reaction resulting from an occupational exposure may be directly reported to Guerbet.

**Severe / Serious:** the term “severe” is often used to describe the intensity (severity) of a specific event (within the scale mild, moderate, severe). The event itself, however, may be of relatively minor medical significance. This is not the same as “serious”, which is based on subject/event outcome or action criteria.

In this protocol, the following situations will not be considered as SAE, providing that they are clearly documented as such in the subject's source data:

- Any hospitalization that had been planned before the study and that will take place during the study, and provided with no aggravation of the disease to which it is related.

 CONFIDENTIAL	Protocol No. LUF-44-001 Version No. 3.0 Date January 20 th 2017	Page 29 / 43
---	--	--------------

- Therapeutic /palliative procedure administration for the study disease (vascular embolization, surgery, radiosurgery etc.) scheduled or not at the time of enrolment, with or without of Lipiodol® Ultra Fluid associated with glues, and provided with no aggravation of the disease to which it is related. Reasons for all those reported procedures will be reviewed by the DSMB in order to ensure of no safety concern and under-reporting.
- Hospitalizations, which are not associated to an AE (such as hospitalization for check up).

### 10.2.2 Procedure for Reporting Serious Adverse Events

SAEs occurring from written informed consent until completion of the study for each subject are to be reported by the investigator to Guerbet Pharmacovigilance department, IRB/IEC ((Institutional Review Board/ Independent Ethics Committee) and Licensing Authority (DCGI). **immediately and within 24 hours** of occurrence of event, using a duly completed SAE report form provided by Guerbet with study documents, even if it is obvious that more data will be needed in order to draw any conclusion.

Guerbet Pharmacovigilance department

- **By Fax #:** [name]
- **Or by e-mail to:** [[contact]](mailto:[contact])

In case of emergency, Guerbet Pharmacovigilance department may be contacted at: **[name]**.

The initial and follow up reports shall identify the study subject by his/her Identification Number assigned for the purpose of the study.

In order to allow the assessment and eventual subsequent regulatory reporting of the case, the following minimum information should be filled in:

- Subject's details including subjects initials, age (or date of birth), gender, weight , height and subject's study enrolment number,
- Description of event by reporting a diagnosis or if not available, symptoms,
- Name of the IMP (generic name) and the name of the surgical glue
- Investigator reporting details

Additional information and/or documentation (e.g. autopsy, outcome, lab reports...) will be required by Guerbet in a timely fashion to ensure accurate follow-up and assessment of each case. This information/documentation should be forwarded, anonymized, with a new SAE report form specifying basic information (follow-up report number, patient details and number, adverse event, IMP, causal relationship) and the new information detailed below (but not limited to):

- Indication(s) for which the mixture was prescribed or tested
- Date and time of onset of the event and of knowledge by study physician
- IMP dosage form, date and time of administration, dose and volume administered, mixture ratio with surgical glue and volume of surgical glue, route of administration,
- End date and time of the event (will be reported in a follow-up report if the event is still ongoing at the time of first notification)
- Subject's medical history relevant to the assessment of the event
- Other treatments: names, indications, dosages, routes of administration, start and end dates and times.
- Expectedness of SAE (expected / unexpected)
- De-challenge and re-challenge when applicable
- Action taken towards the mixture.
- Setting (e.g. hospital/home/nursing home/out patient clinic

 CONFIDENTIAL	Protocol No. LUF-44-001 Version No. 3.0 Date January 20 th 2017	Page 30 / 43
---	--	--------------

- Causal relationship to the mixture
- Causal relationship to the study procedure
- Outcome at the time of reporting
- Treatments
- Date of reporting the event to Licensing Authority and to Ethics Committee overseeing the site

Any event leading to a SAE report should be reported in the medical file and in the AE section of the Case Report Form as requested in Section [10.1.2](#).

SAEs should be followed up by the investigators until complete recovery of the subject or, if not possible, until stabilization of sequelae. The investigator may be requested by Guerbet to provide follow-up information in order to comply with current regulations as well as for comprehensive assessment purposes.

SAEs associated with study procedures are to be notified using the same reporting procedure as described above.

In addition, if occurring after the end of the subject's follow-up period defined for this study (i.e. 30+-3 days after the last procedure of vascular embolization), serious adverse and/or unexpected events that the Investigator thinks may be related to the mixture must be reported to Guerbet regardless of the time between the event and the end of the study.

According to local requirements, the investigator and Guerbet or its representatives will communicate relevant safety information to the appropriate agency(ies), IRB/IEC and/or all active investigators, as it becomes available.

In cases of serious adverse events, the Investigator and Guerbet shall forward their reports after due analysis, to the Chairman of the Ethics Committee, Licensing Authority (DCGI office) and Head of Institution where the trial has been conducted within 14 calendar days of occurrence of the serious adverse event.

The transmission of the information to Guerbet does not release the investigator from his responsibility to inform the regulatory authorities.

